7.1.1. Primary Efficacy Data

The primary efficacy endpoint in the study is the mean of Total Nasal Symptom Score [TNSS (2 to 6 hours)] during a birch allergen EEU challenge at day 29. The primary comparison will be in participants receiving REGN5713-5714-5715 versus placebo.

7.1.2. Secondary Efficacy Data

Secondary endpoints, specified without order, are:

Out-of-season Birch EEU challenges: Symptom endpoints (Part A)

- The mean of symptom scores during out-of-season birch allergen EEU challenges at days 29, 57, and 85
 - TNSS (2 to 6 hours)
 - TOSS (2 to 6 hours)
 - TSS (2 to 6 hours)
- The change and percent change from pre-treatment baseline in symptom scores (TNSS [2-6 hours], TOSS [2-6 hours] and TSS [2-6 hours]) during out-of-season birch allergen EEU challenges at days 29, 57, and 85

• The proportions of participants achieving different degrees of clinical responses will be compared across different symptom response thresholds (TNSS [2-6 hours], TOSS [2-6 hours] and TSS [2-6 hours]) at days 29, 57, and 85

Out-of-season Oak EEU challenge: Symptom endpoints (Part A)

(Note: Day 36 oak EEU challenges are performed only in the subgroup of oak allergic participants, [developed a TNSS of at least 6 out of 12 at 2 or more timepoints during the screening oak EEU at visit 3])

- The mean of symptom scores (TNSS [2-6 hours], TOSS [2-6 hours] and TSS [2-6 hours]) during out-of-season oak allergen EEU challenge at day 36
- The change and percent change from pre-treatment baseline in symptom scores (TNSS [2-6 hours], TOSS [2-6 hours] and TSS [2-6 hours]) during an oak allergen EEU at day 36

Titrated skin prick test endpoints (parts A and B)

- The change and percent change from pre-treatment baseline at days 29, 57, 85 and 127 in the birch, alder and red oak titrated SPT *mean wheal diameter* AUC
- The proportions of participants achieving different degrees of responses in the birch, alder and red oak titrated SPT *mean wheal diameter* AUC will be compared across different response thresholds at days 29, 57, and 85
- The change and percent change from pre-treatment baseline to end-of-season and end-of-study (EOS) visits in the birch (and related allergens) titrated SPT *mean wheal diameter* AUC

Peak season EEU challenge: Symptom endpoints (Part B)

(Note: Peak season EEU is an in-season challenge corresponding to approximate timing of the peak BPS)

• The mean of symptom scores (TNSS [2-6 hours], TOSS [2-6 hours] and TSS [2-6 hours]) during the peak-season birch allergen EEU challenge

In-season field data during birch pollen season (BPS) and peak BPS (Part B)

- The daily symptom and medication scores (CSMS, TSS, TNSS, TOSS, and DMS), averaged during the BPS and peak BPS
- The change and percent change from pre-treatment and pre-season baseline in the symptom and medication scores (CSMS, TSS, TNSS, TOSS, and DMS), averaged during the BPS and peak BPS
- The mean of the total RQLQ(S) score during BPS and peak BPS
- Change and percent change from pre-treatment and pre-season baseline in the RQLQ(S) score during BPS and peak BPS

Drug Concentration, Safety and Immunogenicity (Part A and Part B)

- Incidence rates of treatment-emergent adverse events (TEAEs) and serious TEAEs through EOS
- Total REGN5713, REGN5714, and REGN5715 concentration in serum over the duration of the study
- Incidences and titers of ADA to REGN5713, REGN5714, and REGN5715 over time

7.1.3. Exploratory Efficacy Data

Exploratory endpoints, specified without order, are:

- The mean of symptom scores (TNSS [2-6 hours], TOSS [2-6 hours] and TSS [2-6 hours]) during end-of-season birch allergen EEU challenge (visit 14)
- Within participant comparisons of the treatment effect of anti-Bet v 1 antibodies or placebo to reduce allergic symptoms between the EEU challenges (out-of-season and in-season) and the field, as estimated by the correlation coefficient, mean difference, and heteroscedasticity calculated on the following metrics:
 - Average symptom scores for TNSS (2-6 hours), TOSS (2-6 hours), TSS (2-6 hours) in a birch pollen EEU as compared to average symptom score for TNSS, TOSS, TSS during the BPS and peak BPS
 - Change and percent change from pre-treatment baseline for TNSS (2-6 hours),
 TOSS (2-6 hours),
 TOSS (2-6 hours) in birch pollen EEU challenges
- Within participant comparisons of the treatment effect of the anti-Bet v 1 antibodies or placebo to inhibit the skin test reactivity (using birch and related allergen titrated SPTs), as estimated by the correlation coefficient, mean difference, and heteroscedasticity calculated on the following metrics:
 - Change and percent change from pre-treatment baseline for titrated SPT mean wheal diameterAUC
- The pooled estimate for symptom scores (TNSS, TOSS and TSS) during peak-season birch allergen EEU challenge and daily scores during the BPS
- The daily symptom and medication scores (CSMS, TSS, TNSS, TOSS, and DMS), averaged during the OPS
 - CSMS, TSS, TNSS, TOSS, and DMS, averaged during the OPS
 - The change and percent change from pre-treatment and pre-season baseline in the symptom and medication scores, averaged during the OPS
- The incidence and severity of allergic reactions upon consumption of a food associated with birch pollen food allergy syndrome in participants receiving anti-Bet v 1 antibodies

7.2. Analysis of Efficacy/Pharmacodynamic Data

Six comparisons between treatment groups will be made:

- 1. REGN5713-5714-5715 versus placebo
- 2. REGN5713-5715 versus placebo
- 3. REGN5715 vs placebo
- 4. REGN5713-5714-5715 versus REGN5715 (numerical comparison)
- 5. REGN5713-5714-5715 versus REGN5713-5715 (numerical comparison)
- 6. REGN5713-5715 versus REGN5715 (numerical comparison)

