The effect of REGN5713-5714-5715 on early phase skin responses following titration skin prick test (SPT) with serial dilutions of birch allergen was observed up to 4 months post-dose, as measured by a significant reduction in the AUC of the SPT mean wheal diameters relative to placebo (placebo-adjusted percent changes relative to the baseline SPT of -72.39%, -65.61%, -77.90%, and -73.56% on study days 8, 29, 57, and 113, respectively). Overall, REGN5713-5714-5715 was well tolerated, with no anaphylaxis or evidence of systemic hypersensitivity observed.

A phase 3, randomized, double-blind, placebo-controlled clinical study (R5713-5714-5715-ALG-2001) in 353 birch-allergic participants has been completed. The primary endpoint, daily Combined Symptom and Medication Score (CSMS [TSS+DMS]), averaged over the duration of birch pollen season, met statistical significance. Numerical improvements were observed in TNSS, Total Ocular Symptom Score (TOSS), Daily Medication Score (DMS), and Total Symptom Score (TSS [TNSS+TOSS]); these improvements were more

pronounced during peak season and for participants dosed ahead of the birch season. Robust suppression of skin prick test to birch (and birch-related allergens) was observed in the overall population. REGN5713-5714-5715 900 mg was well tolerated in this subject population. The majority of TEAEs were mild or moderate in intensity and resolved without sequelae. The incidence of SAEs was low and none were deemed related to REGN5713-5714-5715; there were no deaths or adverse events of special interest (AESIs; no severe or systemic hypersensitivity reactions or severe injection site reactions). No new safety signal was observed and overall, REGN5713-5714-5715 900 mg SC had a favorable safety profile.

Taken together, these clinical studies, during experimental and natural exposure to birch pollen, support the use of REGN5713-5714-5715 in the prevention of allergic symptoms in patients with birch pollen allergy upon exposure to birch pollen. The main purpose of this study is to confirm that a combination of all 3 antibodies is required for maximal treatment effect due to broader epitope coverage when 3 antibodies are utilized together.

Additional background information on the study drug and development program can be found in the Investigator's Brochure.

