3. HYPOTHESIS AND RATIONALE

3.1. Hypotheses

Part A Hypotheses:

- A single dose of a cocktail of 3 anti-Bet v 1 monoclonal antibodies (REGN5713-5714-5715) is more effective than placebo in the reduction of allergic nasal symptoms in a birch allergen EEU and in the reduction of skin test reactivity.
- A single dose of a cocktail of 2 anti-Bet v 1 monoclonal antibodies (REGN5713-5715) is more effective than placebo in the reduction of allergic nasal symptoms in a birch allergen EEU and in the reduction of skin test reactivity.
- A single dose of a single monoclonal antibody (REGN5715) is more effective than placebo in the reduction of allergic nasal symptoms in a birch EEU and in the reduction of skin test reactivity.
- A single dose of the 3 anti-Bet v 1 monoclonal antibodies (REGN5713-5714-5715) is more effective than the cocktail of 2 anti-Bet v 1 monoclonal antibodies (REGN5713-5715) and single REGN5715 mAb in a birch EEU as indicated by a numerically greater treatment effect across different endpoints (including allergic nasal and ocular symptoms as well as skin test reactivity), in addition to a higher proportion of participants achieving greater responses across different thresholds for these endpoints.
- Similarly, a single dose of the cocktail of 2 anti-Bet v 1 monoclonal antibodies (REGN5713-5715) is more effective than the single monoclonal antibody (REGN5715) in a birch EEU as indicated by a numerically greater treatment effect across different endpoints, in addition to a higher proportion of participants achieving greater responses across different endpoint thresholds.

Part B Hypotheses:

- REGN5713-5714-5715 is more effective than placebo in the reduction of allergic symptoms during the natural birch pollen season and in the reduction of skin test reactivity to birch allergen.
- REGN5713-5715 is more effective than placebo in the reduction of allergic symptoms during the natural birch pollen season and in the reduction of skin test reactivity to birch allergen.
- REGN5715 is more effective than placebo in the reduction of allergic symptoms during the natural birch pollen season and in the reduction of skin test reactivity to birch allergen.

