3.2. Rationale

3.2.1. Rationale for Study Design

R5713-5714-5715-ALG-21111 is a 2-part randomized, double-blind, placebo-controlled study in birch-allergic participants to assess the efficacy of the anti-Bet v 1 monoclonal antibodies. The study will assess the efficacy of the anti-Bet v 1 monoclonal antibodies, in combination (the 3-mAb and the best 2-mAb) and as a single best antibody (REGN5713-5714-5715, REGN5713-5715, and REGN5715). The efficacy will be tested out-of-season (Part A) as well as in-season (Part B) to fully evaluate treatment effects during experimental exposure to the allergen but also explore them during real-world exposure to birch and other related/ unrelated pollens during the birch pollen season.

Day 29 was chosen as the primary endpoint as a period of expected maximum efficacy, also anticipated to coincide with approximate timing for the peak pollen season. Treatment effects will be evaluated at different out-of-season time points to ensure adequate coverage during an expected natural season accounting for the potential variability between timing of dosing relative to the start of the natural birch pollen seasons and also the year-to-year variability in the length and timing of the birch pollen seasons (Biedermann, 2019c) (Lo, 2019).

Primary efficacy analyses may be performed after all participants complete at least the day 29 EEU challenges or discontinue (Section 10.4.3). Participants will receive the same treatment in Part B that they were originally randomized to receive in Part A (Section 7.5). Additionally, efficacy and safety of repeat dosing of the antibodies will be evaluated during the birch pollen season.

A combination of pre-specified endpoints in Part A (Section 10.4.3) will be used to delineate the contribution of components.

Rationale for the 2-Part "Hybrid" EEU and Field Study Design to Assess the Efficacy of the Anti-Bet v 1 Monoclonal Antibodies in the Reduction of Clinical Symptoms and Skin Test Reactivity

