10.4.3. Efficacy Analyses

Part A data (as described below) will be used to evaluate the efficacy of the anti-Bet v 1 antibody(ies) and delineate the contribution of components using comparisons with placebo and between active treatment arms:

- a. Assess the efficacy in the reduction of allergic symptoms during birch EEU challenges and birch skin test reactivity (TNSS [2 to 6 hours], TOSS [2 to 6 hours], TSS [2 to 6 hours]) and titrated SPT AUC] to determine treatment effects and durability of response.
- b. Compare the proportions of birch-allergic participants achieving different degrees of clinical responses (TNSS [2 to 6 hours], TOSS [2 to 6 hours], TSS [2 to 6 hours] and titrated birch SPT AUC) across different response thresholds to evaluate the benefit of added epitope coverage.
- c. In the subpopulation of oak-allergic participants, assess the treatment effect in the reduction of allergic symptoms during the oak EEU challenge and oak skin test reactivity (TNSS [2 to 6 hours], TOSS [2 to 6 hours], TSS [2 to 6 hours] and titrated oak SPT AUC) at day 36 to evaluate clinical efficacy against oak

Other relevant differences identified between the antibody combinations may also be considered in the decision-making process.

Six comparisons between treatment groups can be made:

- 1. REGN5713-5714-5715 versus placebo
- 2. REGN5713-5715 versus placebo
- 3. REGN5715 vs placebo
- 4. REGN5713-5714-5715 versus REGN5715
- 5. REGN5713-5714-5715 versus REGN5713-5715
- 6. REGN5713-5715 versus REGN5715

These 6 comparisons may be applied for efficacy endpoints. Additional details will be provided in the statistical analysis plan (SAP).

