7.2.2. Analyses of Secondary Endpoints

The secondary continuous efficacy endpoints will be analyzed in a manner similar to that described above (Section 7.2.1.1 Table 2) for the primary efficacy endpoint analysis unless further specified in Table 3. In addition, MI will only be applied for endpoints measured at Day 29.

The proportions of participants achieving different degrees of clinical responses and percent change from pre-treatment baseline in TNSS (2 to 6 hours), TOSS (2 to 6 hours), and TSS (2 to 6 hours) will be compared numerically and graphically using the cumulative distribution function. Participants receiving different combinations of the anti-Bet v 1 antibodies in those receiving

REGN5713-5714-5715, REGN5713-5715, or REGN5715 will be compared with placebo, as well as the comparison between any two active groups. The minimum percent improvement in relevant score will be plotted on the horizontal axis and proportion of participants will be plotted on the vertical axis for each treatment group separately. The AUC of the responder curves derived using the trapezoidal rule will also be calculated as a descriptive summary to compare across different symptom thresholds [as well as including response thresholds such as 30%, 50%, 60%, 75% and 90%], at days 29, 57, and 85 after receiving a single dose of REGN5713-5714-5715, REGN5713-5715, or REGN5715.

The proportions of participants achieving different degrees of change and percent change from pre-treatment baseline in the birch (and related allergens) titrated SPT *mean wheal diameter* AUC will be compared graphically using the cumulative distribution function. The AUC of the responder curves may also be calculated as a descriptive summary to compare across different thresholds [as well as including response threshold such as 30%, 50%, 60%, 75% and 90%] at days 29, 57, 85 in participants receiving REGN5713-5714-5715, REGN5713-5715, or REGN5715.

Subgroups listed in Section 7.2.1.3 might also be applied for secondary endpoints for exploratory analysis. Additional potential sub-group analyses for in-season data:

- Grass sensitization status
- Timing of receipt of dose #2 relative to the local BPS (prior to the season start or after season start), as applicable
- The interval between dose #1 and dose #2 (the cutoff will be decided by the distribution of data, e.g., the median may be used), as applicable

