14. APPENDIX

14.1. Summary of Statistical Analyses

Efficacy/PD Analysis:

Endpoint	Analysis Populations	Primary Analysis	Statistical Method	Supportive Analysis	Subgroup Analysis	Other Analyses
Primary E	ndpoint					
EEU TNSS (2- 6 hours)	FAS	Mean at day 29 for 3-mAb versus placebo	ANCOVA model with treatment group and stratification factors as fixed effect and the baseline mean TNSS (2 to 6 hours) at visit 2 as a covariate.	Yes, sensitivity and supplemental analysis described in Section 7.2.1.2	Yes, subgroups are listed in Section 7.2 .1.3	Plots
Secondary	Endpoints					
EEU (2-6 hours): TNSS, TOSS, TSS	FAS	Mean, change and percent change from pre-treatment baseline, at days 29*, 57, 85 for each of anti-bet v 1 monoclonal antibodies versus placebo	Same as above	No	No	Numerical comparison between three anti-bet v 1 monoclonal antibodies.
EEU (2-6 hours): TNSS, TOSS, TSS	FAS with subjects allergic to oak	Mean, change and percent change from pre-treatment baseline, at days 36 for each of anti-bet v 1 monoclonal antibodies versus placebo	Same as above	No	No	Comparison between combined active group versus placebo
EEU (2-6 hours): TNSS, TOSS,	FAS - B	Mean for each of anti-bet v 1 monoclonal antibodies versus placebo	Same as above	No	No	No
CSMS, TSS, TNSS, TOSS, DMS	FAS - B	Mean, change and percent change from pre-treatment and pre-season baseline, in BPS, peak BPS for each of anti-bet v 1 monoclonal antibodies versus placebo	Same as above except for the average pollen count during local BPS will also be used as a covariate in the model.	No	No	Analyses using 30 grains/ m³ as the cutoff for defining BPS start and end

Endpoint	Analysis Populations	Primary Analysis	Statistical Method	Supportive Analysis	Subgroup Analysis	Other Analyses
RQLQ(S)	FAS - B	Mean, change and percent change from pre-treatment and pre-season baseline, in BPS, peak BPS for each of anti-bet v 1 monoclonal antibodies versus placebo	Same as above	No	No	No
Titrated SPT MWD AUC	FAS for Day 29, 57, and 85 FAS with visit 10 performed at least 12 weeks after dose #1 for Day 127	Change and percent change from pretreatment baseline, at days 29, 57, 85 and 127 for each of antibet v 1 monoclonal antibodies versus placebo	Same as above	No	No	Plots; Numerical comparison between three anti-Bet v 1 monoclonal antibodies.

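### The SAP commits to no 95% confidence interval for the active-versus-active comparisons that are meant to show what each antibody contributes

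*SAP*

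**What the plan says.** Protocol section 1 gives the aim as follows: "The main purpose of this study is to confirm that a combination of all 3 antibodies is required for maximal treatment effect". Protocol 10.4.3 says that Part A data will "delineate the contribution of components using comparisons with placebo and between active treatment arms", and the comparison of the active arms is a secondary objective in protocol 2.2.

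The criterion is in protocol 3.1. The 3-antibody cocktail is taken to be more effective than the other two active arms "as indicated by a numerically greater treatment effect across different endpoints (including allergic nasal and ocular symptoms as well as skin test reactivity", together with higher responder proportions. A parallel statement covers the 2-antibody arm against the single antibody.

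SAP 7.2 lists six comparisons. The three against placebo carry no qualifier. The three between active arms are marked as numerical, for example "REGN5713-5714-5715 versus REGN5713-5715 (numerical comparison". SAP 14.1 repeats this in its column for other analyses: "Numerical comparison between three anti-bet v 1 monoclonal antibodies". For responder proportions, SAP 7.2.2 says the groups "will be compared numerically and graphically using the cumulative distribution function", and it includes any pair of active arms.

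On precision, SAP 7.2.1.1 provides LS means for each treatment group, but names a difference with a p-value and 95% interval only for the 3-antibody arm against placebo. The hierarchy in SAP 8.2 contains only comparisons with placebo.

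**The concern.** Whether a second and a third antibody add anything is a question about differences between active arms. Beating placebo in each arm does not answer it. Nor does finding one arm significant against placebo and another not.

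A numerical comparison shows which arm did better and by how much, but not whether the gap is distinguishable from zero. If two active arms are truly equal, one of them is still numerically ahead on any given endpoint about half the time. Following the plan as written, a reader could take a small advantage as a component contribution when the data are equally consistent with none. The interval also works in the other direction, because it shows how large a contribution the data can rule out.

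Trial success is not at stake, since it depends only on the 3-antibody arm against placebo. What is at stake is how firmly the report can speak on the purpose stated in protocol section 1.

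**Working it through.** **Inputs.** From protocol 10.2 and SAP 2.2: common SD 2.8; planned difference from placebo 1.61 TNSS points (5.35 minus 3.74); two-sided 5% level; two-sample t-test; 65 per arm for 90% power; 73 per arm after 10% dropout; minimum detectable difference 1.0. SAP 2.2 adds 50 per arm for about 80% power. The documents give no expected difference between active arms, no correlation between baseline and day-29 TNSS, and no SD for the titrated SPT AUC.

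**The plan's own figures.** With the noncentral t distribution, power for a difference of 1.61 is 89.8% at 64 per arm and 90.2% at 65, so 65 is the smallest sample size that reaches 90%. Power at 50 per arm is 81.2%. Dropout: 65 / 0.9 = 72.2, rounded up to 73. The smallest observed difference that reaches significance at 65 per arm is 0.97, against the stated 1.0. All reproduce, and all concern the 3-antibody arm against placebo.

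**Interval for an active-versus-active difference in day-29 TNSS.** Half-width = t(0.975, 2n − 2) × SD × √(2/n).

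- n = 65: 1.979 × 2.8 × √(2/65) = 1.979 × 0.491 = 0.97.
- n = 50: 1.984 × 2.8 × √(2/50) = 1.984 × 0.560 = 1.11.
- In SD units, t × √(2/n) is 0.35 at 65 per arm and 0.40 at 50. This form also applies to the SPT AUC.

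**Gain from baseline adjustment.** The half-width is multiplied by √(1 − ρ²), where ρ is the baseline correlation (assumed).

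| Assumed ρ | 65 per arm | 50 per arm |
|---|---|---|
| 0 | 0.97 | 1.11 |
| 0.3 | 0.93 | 1.06 |
| 0.5 | 0.84 | 0.96 |
| 0.7 | 0.69 | 0.79 |

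The planned model fits four arms together and combines imputations at day 29, so the actual widths will differ somewhat.

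**Illustration.** Take a difference of a quarter of the planned placebo effect: 0.25 × 1.61 = 0.40 (assumed).

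- Observed at 65 per arm, unadjusted: 0.40 ± 0.97, that is −0.57 to 1.37. It meets a numerically-greater criterion and is compatible with zero.
- If 0.40 were the true difference at 65 per arm, the observed direction would favour the 3-antibody arm with probability Φ(0.4025/0.491) = 79%, or 83% with ρ = 0.5. The 95% interval would exclude zero in its favour only 13% to 15% of the time.

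**The case against.** The strongest reply is that this is an open and consistent design choice. Protocol 3.1 states the numerical criterion, power is claimed only for the 3-antibody arm against placebo, and the SAP follows suit. That stands: there is no contradiction between the documents, and the absence of a powered test between active arms is not a defect.

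A second reply is that the interval may be coming anyway. SAP 7.2.2 analyses secondary endpoints much like the primary one, and SAP 14.1 places the numerical comparisons in rows whose method is the ANCOVA. Read strictly, SAP 7.2.1.1 would also deny an interval to the 2- and 1-antibody arms against placebo, which are formally tested in 8.2, so its list is not exhaustive. This stands in part. One cannot say that intervals will be withheld, only that the SAP does not commit to them and leaves the term numerical undefined.

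Three stronger readings are tempting, and the documents do not support them.

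- A reader might infer that no between-arm difference will be available. In fact, group summaries (SAP 4), LS means (7.2.1.1) and distribution curves (7.2.2) show the size of each difference. Only the model-based precision is uncommitted.
- A reader might infer that component claims rest on comparisons 4–6 alone. Protocol 10.4.3 also uses the placebo comparisons, and SAP 8.2 tests each active arm against placebo on two endpoints.
- A reader might infer that a rule is needed for how many endpoints must agree. Protocol 3.2.1 says "A combination of pre-specified endpoints in Part A (Section 10.4.3) will be used to delineate the contribution of components", and 10.4.3 adds "Other relevant differences identified between the antibody combinations may also be considered in the decision-making process". No count is given, but a descriptive judgement across named endpoints is legitimate, and a mandatory rule would narrow protocol text. Chance agreement is also less alarming than it may look. In simulation with three equal active arms, the full order of 3 over 2 over 1 antibodies on all four day-29 endpoints (TNSS, TOSS, TSS, SPT AUC) arises 1% to 3% of the time. That assumes a TNSS:TOSS SD ratio of 2:1, a TNSS–TOSS correlation of 0.5 or 0.8, and an SPT–symptom correlation of 0 to 0.5.

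**Conclusion.** The point holds as a gap in reporting. The plan lets one active arm be called more effective on a numerical advantage and does not commit to an interval for that contrast. On the documents' SD and sample sizes, an observed day-29 TNSS advantage below about 0.97 points at 65 per arm, or 1.11 at 50, would have an unadjusted 95% interval that includes zero. With an assumed baseline correlation of 0.5 these thresholds fall to 0.84 and 0.96. They compare with 1.61 planned against placebo, so a contribution of half the placebo effect (0.81) would still be inside them.

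The half-widths rest on the planning SD of 2.8; the adjusted ones also rest on an assumed correlation. The 0.40 example is an illustration, not a forecast. The point does not touch the primary analysis or type I error control, and it calls for no formal test. It is a cheap improvement.

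**What to change.** In SAP 7.2 and 14.1, state that comparisons 4–6 are reported as LS-mean differences with unadjusted 95% confidence intervals from the planned four-arm ANCOVA, combined over imputations at day 29. Cover the birch EEU symptom scores and the birch titrated SPT mean wheal diameter AUC. Label the intervals descriptive and outside the section 8.2 hierarchy, and say that statements on component contribution are read together with them. The wording is best settled before the Part A unblinding described in SAP 1.3.

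The cost is SAP text and table shells. The contrasts come from a model already planned. No alpha, added participants, endpoint-agreement rule or change to the protocol hypotheses is needed. The downside is that the intervals will be wide, so some statements about components will have to be weaker.
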